4.2 General Presentation Considerations

All efficacy and safety variables will be summarised by study treatment group using descriptive statistics. For continuous variables, descriptive statistics will include the number of participants (n), mean, SD, median, minimum and maximum. For log-normal variables, descriptive statistics will include n, mean, SD, median, minimum, maximum, geometric mean (GeoMean), and coefficient of variation (CV). Categorical variables will be summarised using frequencies and percentages. Continuous data that are expected to be skewed will be presented in terms of the maximum, upper quartile, median, lower quartile, minimum and number of observations. The minimum and maximum will be reported to the same number of decimal places as the raw data recorded in the database. The mean, median, lower quartile, and upper quartile will be reported to one more decimal place than the raw data recorded in the database. The SD will be reported to two more decimal places than the raw data recorded in the database. In general, the maximum number of decimal places reported shall be four for any summary statistic.

Percentages will be presented to one decimal place. Percentages will not be presented for zero counts. Percentages will be calculated using n as the denominator, unless otherwise specified. If sample sizes are small, the data displays will show the percentages, but any textual report will describe frequencies only.

Changes from baseline in categorical data will be summarised using shift tables where appropriate. P-values greater than or equal to 0.001, in general, will be presented to three decimal places. P-values less than 0.001 will be presented as “<0.001”.

Confidence intervals (CIs) will be presented to one more decimal place than the raw data.

Data will be summarised by-visit as applicable.

‘Baseline’ is defined as the last value obtained prior to the first dose of study medication, unless otherwise stated. ‘End of Study’ is defined as the last available post-treatment assessment. ‘Study Day’ will be calculated relative to the date of randomisation, ie:

If Assessment Date < Randomisation Date, then

$$\text{Study Day} = \text{Assessment Date} - \text{Randomisation Date}$$

If Assessment Date ≥ Randomisation Date then

$$\text{Study Day} = \text{Assessment Date} - \text{Randomisation Date} + 1$$

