4.5.1 Analysis Sets

Analysis sets consist of two components: (1) analysis population (See Section 4.5), which specifies the participants included in an analysis; (2) data period, defining the time period during which data will be included in the analysis.

Analysis Set	Analysis Population	Data Period
Full Analysis Set	Full Analysis Population	Day 1 to the end of the follow-up period
Per-Protocol Set	Per-Protocol Population	Day 1 to the end of the follow-up period
Safety Analysis Set	Safety Analysis Population	Day 1 to the end of the follow-up period
Monotherapy Safety Analysis Set	Safety Analysis Population	Day 1 to the end of the first treatment period
Extended Safety Analysis Set	Extended Safety Analysis Population	Day 1 to the end of the follow-up period with flag to subset Week 12 to the end of the follow-up period

The Extended Safety Analysis Set includes participants who entered the second treatment period. The Week 12 flag is added to the Extended Safety Analysis Set to allow subsetting of participant data to be from Week 12 to end of study.

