4.10 Safety Evaluation

All safety summaries and analyses will be based upon the Safety analysis set as defined in Section 4.5, unless otherwise specified. Safety summaries will be presented by treatment group and with a pooled AZD5718 group, where appropriate.

Change from baseline will be calculated as the differences between the post-dose value at each time point and the value prior to administration of the study medication.

Individual safety and tolerability data will be provided in data listings and summarised as appropriate by treatment and overall. Continuous variables (laboratory parameters, ECG, and blood pressure) will be summarised using descriptive statistics (n, mean, SD, minimum, median, and maximum) as appropriate by scheduled assessment time point. Where applicable, data will be summarised for the observed value, and for the corresponding change from baseline/screening. Categorical variables will be summarised in frequency tables (counts and percentage) as appropriate by scheduled assessment time point too.

Outputs presented on the Extended Safety Analysis Set will include the Week 12 flag to subset for data in the second treatment period. These outputs may be repeated without the Week 12 flag if deemed appropriate by the study team, thereby including all data for participants who continued into the second treatment period only.

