4.10.4 Clinical Laboratory Evaluation

The following summaries will be provided:

- A summary of the observed absolute values and change from baseline in each haematology and clinical chemistry laboratory parameter by treatment group and time point.
- A summary of baseline versus maximum observation on treatment in each laboratory parameter by treatment group (shift table)
- A summary of baseline versus minimum observation on treatment in each laboratory parameter by treatment group (shift table)
- A summary of key participant information for participants reporting changes outside reference ranges in each laboratory parameter
- A summary of the number and percentage of participants reporting changes outside reference ranges in each laboratory parameter
- A plot of alanine aminotransferase (ALT) versus total bilirubin, expressed as multiples of upper limit of normal (ULN)
- A plot of aspartate aminotransferase (AST) versus total bilirubin, expressed as multiples of ULN
- A plot of liver biochemistry over time, for participants with potential Drug Induced Liver Injury (ie, $ALT/AST \geq 3 \times ULN$ and total bilirubin (BILI) $\geq 2 \times ULN$, and in which the elevation in transaminases precede or coincide with (that is, on the same day as) the elevation in BILI or $ALT/AST \geq 5 \times ULN$)
- A summary of the number and percentage of participants reporting maximum on-treatment ALT and AST by maximum total bilirubin for assessing Hy's Law criteria
- A summary of individual participant data for participants with Potential Hy's Law ie, participants with combined ALT or AST, and bilirubin elevations
- A summary of treatment-emergent laboratory changes will be presented for the Safety Analysis Set, the Monotherapy Safety Analysis Set (Treatment Period 1) and the Extended Safety Analysis Set with Week 12 flag (Treatment Period 2).

Treatment-emergent laboratory and vitals change (TELVC) limits of interest for this study are provided in [Appendix C](#) for the laboratory parameters, and in [Table 5](#) for vital signs.

By-participant listings of all laboratory data will be provided including participant identifier, treatment, age, sex, race, visit, category, laboratory test name, result, and standard units. Laboratory reference ranges will also be listed and out of range values will be flagged.

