- o Sites should ensure that the validity criterion described in Section 8.2.5 (CSP) is met prior to completing any other assessments at the visit. If the validity criterion is not met, the associated study visit may be rescheduled to allow for a repeat ABPM recording only if the rescheduled visit can be completed within the specified tolerance period for study visits:
- Visit 3: up to 72 hours following the originally scheduled visit for Visit 3 but no more than 32 days from Screening Visit 1.
 - Visit 7: ± 72 hours from Day 85.
- If a repeat ABPM session is not possible, the study visit should proceed as indicated. In addition, the visit should also continue if the ABPM session does not meet the validity criterion after the repeat session.
- p Study drugs refer to AZD5718/placebo during Treatment Period 1 and AZD5718/placebo + dapagliflozin during Treatment Period 2.
- q Site should follow-up directly with the participant via phone to remind the participant.
- r Participants to return all study drug dispensed at previous visits and only use the newly dispensed study drug. Participants should be reminded not to take study drug on the days of a study visit until instructed by the study site.

NOTE: All laboratory assessments are to be performed in central laboratories, except for tests completed using dipsticks and drug and alcohol screen tests which will be done locally. Laboratory kits used locally will be provided by the central laboratory.

NOTE: Where the values for the following investigations are outside the usual range for a participant during screening, based on their medical history, retesting may be undertaken on one occasion without requiring a re-screen: Blood pressure, eGFR, spot urine for ACR, ALT, AST, bilirubin, and serum potassium.

Abbreviations: ABPM = ambulatory blood pressure monitoring; ACR = albumin to creatinine ratio; AEs = adverse events; ALT = alanine aminotransferase; AST = aspartate aminotransferase; BMI = body mass index; CKD = chronic kidney disease; CSP = clinical study protocol; DKD = diabetic kidney disease; ECG = electrocardiogram; e-Diary = electronic Diary; eGFR = estimated glomerular filtration rate; FSH = follicle stimulating hormone; fT3=free triiodothyronine; fT4=free thyroxine; h = hour, HbA1c = glycated haemoglobin; hCG = human chorionic gonadotropin; LH = luteinising hormone; **CCI**; PK = pharmacokinetic(s); SAEs = serious adverse events; TSH=thyroid stimulating hormone.

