Appendix C: Treatment-Emergent Laboratory and Vital Signs Criteria limits

The treatment-emergent laboratory and vitals change (TELVC) limits of interest for this study are as follows:

Laboratory Parameter	Range	TELVC limits
Creatinine		≥ 1.5 x Baseline Serum Creatinine ≥ 2 x Baseline Serum Creatinine
Sodium		< 120 mmol/L < 130 mmol/L > 150 mmol/L
Potassium		≤ 2.5 mmol/L ≥ 6.0 mmol/L
Creatine Kinase		> 5 x ULN > 10 x ULN

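### The Period 2 laboratory-change table keeps the pre-first-dose baseline, so creatinine rises that began wholly or partly before dapagliflozin are counted as emerging in Period 2

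*SAP*

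**What the plan says.** SAP 4.2 sets the general rule: baseline "is defined as the last value obtained prior to the first dose of study medication, unless otherwise stated". SAP 4.10 repeats it for safety data. Change is the difference between "the post-dose value at each time point and the value prior to administration of the study medication", and summaries are given for observed values and "for the corresponding change from baseline/screening". Week 12 is not named as a reference.

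SAP 4.10.4 then presents treatment-emergent laboratory changes on the whole Safety Analysis Set and also on "the Monotherapy Safety Analysis Set (Treatment Period 1) and the Extended Safety Analysis Set with Week 12 flag (Treatment Period 2"). SAP 4.10 explains the flag: "Outputs presented on the Extended Safety Analysis Set will include the Week 12 flag to subset for data in the second treatment period". SAP 4.5.1 says that it serves "to allow subsetting of participant data to be from Week 12 to end of study". It selects records and does not reset the baseline.

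Appendix C gives the limits. For creatinine they are "≥ 1.5 x Baseline Serum Creatinine" and twice baseline. For sodium and potassium they are fixed concentrations, and for creatine kinase multiples of the upper limit of normal.

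The treatments are "AZD5718/placebo during Treatment Period 1 and AZD5718/placebo + dapagliflozin during Treatment Period 2" (Appendix A, footnote p).

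**The concern.** A table headed as Period 2 and described as treatment-emergent will be read as showing what emerged once dapagliflozin was added. With the reference fixed before the first dose of AZD5718 or placebo, it does not show that. A creatinine rise that began in Period 1 and persists, or that needs only a small further rise to cross the limit, is counted under the combination.

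For adverse events the SAP avoids this: section 4.10.2 assigns each event to the period in which it starts. Laboratory changes have no such rule. Where the SAP wants a special baseline it states one (urine ACR in 3.2.1.1, ambulatory blood pressure in 4.9.3.3, retinal data in 4.11.2), so silence here leaves the general definition in force.

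At stake is the reading of renal and electrolyte safety before and after the add-on, which is the reason for splitting the table by period.

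**Working it through.** The plan gives no figure on this point to reproduce. The check applies the SAP's rule to assumed creatinine courses and then to an assumed distribution.

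**1. Fixed courses** (Day 1 = 1.00; limit 1.5; Period 2 read at Weeks 16 and 20)

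| Course | Ratio to Day 1 in Period 2 | Flagged, Day 1 baseline | Ratio to Week 12 | Flagged, Week 12 baseline |
|---|---|---|---|---|
| (a) 1.55 from Week 8, unchanged | 1.55 | yes | 1.00 | no |
| (b) 1.3 in Period 1, then a further 1.2 times | 1.3 × 1.2 = 1.56 | yes | 1.20 | no |
| (c) 1.55 only after Week 12 | 1.55 | yes | 1.55 | yes |
| (d) 0.80 in Period 1, then 1.5 times | 0.80 × 1.5 = 1.20 | no | 1.50 | yes |
| (e) 1.55 in Period 1, back to 1.05 by Week 12 | 1.05 | no | 1.00 | no |

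Course (a) is counted in both period tables. In (b) the Period 1 part carries the participant over the limit. In (d) the Period 2 rise is missed. Course (e) shows that a change must persist to Week 12 to be carried over.

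**2. Size under assumptions.** The documents give no creatinine variability, so every input here is assumed. Let A be the log ratio of Week 12 to Day 1, normal with mean 0 and SD 0.15. Let B1 and B2 be the log ratios of Weeks 16 and 20 to Week 12, independent normals with mean ln 1.08 = 0.077 and SD 0.12. The limit is ln 1.5 = 0.4055. The Week 12 value itself and the follow-up visit are left out.

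- Week 12 baseline: P(max(B1, B2) ≥ 0.4055) = 1 − Φ((0.4055 − 0.077)/0.12)² = 1 − Φ(2.74)² = 0.6%.
- Day 1 baseline: P(A + max(B1, B2) ≥ 0.4055) = 7.4%, by simulation.
- Already at the limit at Week 12: 1 − Φ(0.4055/0.15) = 1 − Φ(2.70) = 0.34%. These are at most 0.34/7.4, or 4% to 5%, of those flagged. The other 7.1 points or so first cross the limit in Period 2.

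**3. AZD5718 raising creatinine 10% in Period 1 only.** The mean of A becomes ln 1.10 = 0.095. The Period 2 table shows 17.8% on AZD5718 against 7.4% on placebo with the Day 1 baseline, and 0.6% in both arms with the Week 12 baseline. About 10% of those flagged on AZD5718 were already over the limit at Week 12.

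**4. Range for placebo**

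| SDs (Period 1 / Period 2), rise | Day 1 baseline | Week 12 baseline |
|---|---|---|
| 0.12 / 0.10, 5% | 2.0% | 0.04% |
| 0.15 / 0.12, 8% | 7.4% | 0.6% |
| 0.20 / 0.15, 8% | 15.0% | 2.8% |

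Over this range, 2% to 14% of those flagged were already over the limit at Week 12.

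**5. Sodium, potassium and creatine kinase.** Their limits do not contain the baseline value, so changing the baseline does not move them. A value over the limit at Week 12 that stays there is still counted in Period 2, because nothing requires it to be new.

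**The case against.** The strongest reply is that cumulative change from the pre-treatment value is a legitimate safety quantity, and that a Week 12 reference hides it. In the base case, 6.7% of placebo participants newly reach 1.5 times Day 1 in Period 2 without reaching 1.5 times Week 12; course (b) is an example. This stands as a reason to keep the Day 1 baseline somewhere. It is met because the same summary is planned on the whole Safety Analysis Set, where that baseline remains.

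Other outputs also help a reader to date a change. There are summaries of values and changes by time point, by-participant listings, the Period 1 version of the same table, and an eGFR objective covering Week 12 to Week 20 (although SAP 4.9.3.2 does not spell out a model referenced to Week 12). That limits the harm but does not correct the table's label.

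One could read the wording on study medication in SAP 4.10 as meaning dapagliflozin in Period 2. SAP 4.2 refers to the first dose, and no passage states an exception.

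Three stronger inferences are tempting and are not supported:

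- **That the arm comparison is biased.** All arms add dapagliflozin in Period 2 and are judged by one rule. In step 3 the difference between arms is a real effect measured from Day 1; only its period is wrong.
- **That 7.4% against 0.6% measures double counting.** It mostly contrasts cumulative with incremental change.
- **That all the Appendix C limits depend on baseline.** Only the creatinine limits do.

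**Conclusion.** The point holds for the Week 12-flagged treatment-emergent laboratory summary in SAP 4.10.4; the other laboratory summaries there are not listed by period. As written, that table counts creatinine rises that arose wholly or partly before dapagliflozin, recounts electrolyte and creatine kinase abnormalities that persist from Week 12, and can miss a Period 2 creatinine rise after a Period 1 fall.

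These directions follow from the definitions alone. The percentages rest entirely on assumed variability and rise, and show only that the choice of reference can change the table several-fold. The consequence is misattribution to a period in one descriptive output. It is worth correcting because the correction is cheap, but it does not affect the validity of the randomised safety comparison. Nor would a Week 12 baseline isolate the effect of dapagliflozin, since no arm goes without it in Period 2.

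**What to change.** Add to SAP 4.10.4, with a cross-reference from 4.2, that for the treatment-emergent laboratory change summary on the Extended Safety Analysis Set with the Week 12 flag:

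- the creatinine multiples are computed against the last value before the first dapagliflozin dose, normally Visit 7;
- the sodium, potassium and creatine kinase limits are counted only if not already met at that value;
- the pre-dapagliflozin value serves as the reference and is not itself counted as a Period 2 result, a point that the SAP leaves open because the flag starts at Week 12.

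Keep the Day 1 baseline for the whole-study and Monotherapy tables, and name the baseline in each table title.

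The cost is one derived baseline flag and a few lines of text. No new data are needed, since safety laboratory samples are already scheduled at Visit 7. The downside is that two labelled baselines are in use, and cumulative creatinine rises must be read from the whole-study table.
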